9.2.3.2 Visit 2 (Follow-up 1: 12 weeks from Visit 1)

After 12 weeks from Visit 1, the participant returns for follow-up. The following data will be collected:

- Visit date
- Physical examination information (weight, BMI, blood pressure)
- Concomitant medication use
- Any changes in the JARDIANCE administration status
- Efficacy assessment: UACR (The measurement taken on the date closest to the visit date is collected.)
- Any changes in the laboratory test results (HbA1c, eGFR, serum creatinine, etc.: if available) if there is any lab result which was clinically significant compared to data before JARDIANCE® treatment
- Safety assessment: any AEs noted
- Study completion status (if applicable)
- Investigator's overall efficacy assessment (if applicable)

9.2.3.3 Visit 3 (Follow-up 2: 24 weeks from Visit 1)

After 24 weeks from Visit 1, the participant returns for a final follow-up. The following data will be collected:

- Visit date
- Physical examination information (weight, BMI, blood pressure)
- Concomitant medication use
- Any changes in the JARDIANCE® administration status
- Efficacy assessment: UACR (The measurement taken on the date closest to the visit date is collected.)
- Any changes in the laboratory test results (HbA1c, eGFR, serum creatinine, etc.: if applicable) if there is any lab result which was clinically significant compared to data before JARDIANCE® treatment
- Safety assessment: any AEs noted
- Study completion status
- Investigator's overall efficacy assessment

ONIS New Data Collection Protocol

Page 17 of 54

Study number: 1245-0323 **Document number: c42645766-03**

Proprietary confidential information © 2024 Boehringer Ingelheim International GmbH or one or more of its affiliated companies

9.2.4 Study discontinuation

BI reserves the right to discontinue the study overall or at a particular study site at any time for the following reasons:

- 1. Failure to meet expected enrolment goals overall or at a particular study site
- 2. Emergence of any effectiveness / safety information that could significantly affect continuation of the study, or any other administrative reasons
- 3. Violation of Good Pharmacoepidemiology Practice (GPP), the study protocol, or the contract by a study site, investigator or research collaborator, disturbing the appropriate conduct of the study

The investigator / the study site / research collaborator will be reimbursed for reasonable expenses incurred in case of study / site termination (except in case of the third reason).

Flow Chart 9.2.5

Data points	Baseline	Follow-up 1	Follow-up 2
Visit	1	2	3
Week	0	12	24
Data release consent	X		
Diagnosis	Χ		
Inclusion/Exclusion criteria	Χ		
Demographics (initial, gender,	Χ		
age, smoking status, alcohol			
intake status, history of type 2			
DM)			
Medical history ¹⁾	Χ		
Physical examination (blood	Χ	Х	X
pressure, height ²⁾ , weight, BMI)			
Past ³⁾ or concomitant therapies	Х		
JARDIANCE® administration status	Χ	Х	Х
UACR ⁴⁾	Х	Х	Х
Investigator's overall efficacy		X ^A	Х
assessment			
Other laboratory tests ⁵⁾	X ^B	X ^B	X ^B
AEs		X	Х
Study completion		X ^A	X

A: If applicable

B: If available

¹⁾ Medical history 6 months prior to Visit 1 is collected.

²⁾ Height is measured only in Visit 1.

³⁾ Past medications 1 month prior to Visit 1 are collected.

⁴⁾ Data performed on the date closest to each visit date are collected.

ONIS New Data Collection Protocol

Study number: 1245-0323 Document number: c42645766-03

Page 18 of 54

Proprietary confidential information © 2024 Boehringer Ingelheim International GmbH or one or more of its affiliated companies

5) Data performed on the date closest to each visit date can be collected. Laboratory test results such as eGRF, HbA1c, etc. are collected, if available.

9.3 VARIABLES

9.3.1 Exposures

Exposure to JARDIANCE® will be estimated as time from the first intake date to the last intake date of the participant during the study period.

The treatment dose is based on the current authorized label in Korea. The recommended dose of JARDIANCE® is 10mg once daily and it can be taken with or without food.

9.3.2 Outcomes

9.3.2.1 Primary outcomes

The primary outcomes are the safety outcomes calculated as the incidence of:

- AEs
- Serious adverse event (SAEs)
- Non-serious adverse events
- Adverse drug reaction (ADR)s
- Serious adverse drug reactions
- Unexpected adverse events
- Adverse events of special interest (AESIs)
- Specific adverse events
- Adverse events leading to temporary or permanent discontinuation
- Adverse events by intensity
- Adverse events by outcome of the events
- Adverse events by causality
- Adverse events leading to death

Assessment of safety:

- Adverse events (event name/ symptoms/ sign)
- Onset date, End date
- Intensity (Mild/ Moderate/ Severe)
- Serious (Serious/ Non-Serious)
- Outcome of the event (Recovered/ Not yet recovered/ Sequela/ Fatal/ Unknown)
- Causality (Certain/ Probable·Likely/ Possible/ Unlikely/ Conditional· Unclassified/ Unassessable·Unclassifiable)
- Action taken with study drug due to AE (Dose not changed/ Dose reduced/ Dose increased/ Drug withdrawn/ Not applicable)

ONIS New Data Collection Protocol

Page 19 of 54

Study number: 1245-0323 Document number: c42645766-03

Proprietary confidential information © 2024 Boehringer Ingelheim International GmbH or one or more of its affiliated companies

- Adverse events of special interest (Liver injury, Ketoacidosis in diabetic and nondiabetic population, Lower limb amputation)
- Specific adverse events (Severe hypoglycaemia, Urinary tract infection, Genital infection, Bone fracture, Urinary tract malignancy, Volume depletion, Acute kidney injury, Gout, Hyperkalaemia)

9.3.2.2 Secondary outcomes

The secondary outcome is the efficacy outcome as follows:

Change in UACR from baseline after 12 weeks and/or 24 weeks of treatment

9.3.2.3 Further outcomes

The further outcomes are as follows:

 Progression or reduction in albuminuria* from baseline (defined as a worsening to a more severe UACR category)

*Albuminuria category [P22-08623] is assigned as follows:

		ACR (approxima	te equivalent)	_
Category	AER (mg/24h)	(mg/mmol)	(mg/g)	Terms
A1	<30	<3	<30	Normal to mildly increased
A2	30-300	3-30	30-300	Moderately increased ^a
A3	>300	>30	>300	Severely increased ^b

ACR, albumin-creatinine ratio; AER, albumin excretion rate

 Investigator's overall efficacy assessment after 12 weeks and/or 24 weeks of treatment

The overall efficacy assessment is performed at the investigator's discretion. The information includes:

- Improved: If determined as there is any effect of maintaining or improving clinical condition.
- Unchanged: If clinical condition has not been changed compared with before administration, and not determined as there is any effect of maintaining clinical condition.
- Aggravated: If clinical condition is worse than before administration.
- Unassessable: If clincal condition cannot be determined.

aRelative to young-adult level.

bIncluding nephrotic syndrome (AER usually >2200 mg/24h [ACR >2200 mg/g; >220 mg/mmol]).

ONIS New Data Collection Protocol

Page 20 of 54

Study number: 1245-0323 Document number: c42645766-03

Proprietary confidential information © 2024 Boehringer Ingelheim International GmbH or one or more of its affiliated companies

9.3.3 Covariates

- 1) Participant characteristics
 - Demographics: age, gender, pregnancy status, breastfeeding status, smoking status, alcohol intake status, history of type 2 DM
 - Physical examination results: height, weight, blood pressure, BMI
 - Disease information: duration of disease, medical history, past or concomitant medications
- 2) JARDIANCE® administration status: total duration of administration, total administered dose, average daily dose
- 3) Participants of special investigation: pediatric population, geriatric population, pregnant women, lactating women, hepatic impairment
- 4) Laboratory test results
- 5) Study completion status: follow-up duration, reasons for stopping JARDIANCE® administration

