9.7.2 Safety analysis

Safety analyses will be performed on the safety set.

Frequency of safety events will be reported using numbers of participants with AEs, frequencies, incidence with 95% CIs. AEs will be tabulated by system organ class and preferred term for overall and for subgroup based on demographics and baseline characteristics.

Categorical variables will be reported using numbers of participants with AEs, frequencies, incidence with 95% CIs. Incidence will be analyzed using Pearson's chi-square or Fisher's exact test to determine if there are statistically significant differences.

Continuous variables will be reported using number of participants. Incidence will be reported using odds ratios and 95% CIs by simple logistic regression.

As a result of simple logistic regression, statistically significant variables will be reported using odds ratios and 95% CIs by multiple logistic regression.

AEs will be coded with the current version of the Medical Dictionary for Regulatory Activities (MedDRA). Past / concomitant medications will be coded according to the current version of the Korea Index of Medical Specialties (KIMS) coding system.

Safety analyses will be based on all participants treated, i.e. all participants who received at least one dose of JARDIANCE[®]. However, if data for participants who have been treated with JARDIANCE® beyond the scope of approved label are collected, these will be listed separately.

9.7.3 **Efficacy analysis**

Efficacy analyses will be performed on the efficacy set.

Efficacy analyses will be performed by subgroup based on demographics and baseline characteristics.

The standard descriptive statistical parameters (number of participants, mean, standard deviation, median, minimum, maximum, etc.) will be summarized.

The changes of the efficacy outcomes from baseline will be compared in an exploratory sense via paired t-test.

ONIS New Data Collection Protocol

Page 23 of 54

Study number: 1245-0323 Document number: c42645766-03

Proprietary confidential information © 2024 Boehringer Ingelheim International GmbH or one or more of its affiliated companies

For investigator's overall efficacy assessment, the number and percentage of participants will be presented. If the result of overall assessment is 'improved', it will be classified as 'effective'. If the result of overall assessment is 'unchanged' or 'aggravated', it will be classified as 'ineffective'.

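### Exposure in 9.3.1 includes treatment gaps, and 9.3.3 lists post-baseline duration and dose as covariates, so the regressions can show a false inverse association with AEs

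*Protocol*

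**What the plan says.** Protocol section 9.3.1 defines exposure as "estimated as time from the first intake date to the last intake date of the participant during the study period". Nothing is deducted for time off the drug. Section 9.3.2.1 expects such time, because one primary outcome category is "Adverse events leading to temporary or permanent discontinuation". Section 9.2.3 collects dose, frequency, and start and end dates at Visit 1, and changes in administration at Visits 2 and 3.

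Section 9.3.3 is the only list of covariates. Beside age, gender and medical history it contains "JARDIANCE® administration status: total duration of administration, total administered dose, average daily dose" and, under study completion, "follow-up duration, reasons for stopping JARDIANCE® administration". The list does not mark which items are baseline and which arise after treatment starts.

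For AEs, section 9.7.2 says of continuous variables: "Incidence will be reported using odds ratios and 95% CIs by simple logistic regression". It adds that "statistically significant variables will be reported using odds ratios and 95% CIs by multiple logistic regression". It does not name the variables. The restriction "for subgroup based on demographics and baseline characteristics" is attached to the tabulation by system organ class and preferred term, not to the regression sentences. For the effective rate, section 9.7.3 plans logistic and/or Poisson regression and says that covariates found significant will be interpreted. Section 11.2 collects AEs from consent to the end of the study, not only while the participant takes the drug.

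**The concern.** Duration and total dose are known only once treatment has ended, and an AE can be the reason it ended. A participant who stops because of an AE has a short duration, a low total dose and an AE on record. If duration or total dose is used to explain whether an AE occurred, cause and effect are reversed, and longer use appears to go with fewer AEs even when exposure has no effect on risk. Picking variables for the multiple model by significance favours such an artefact. The primary objective is safety monitoring, so this error points towards false reassurance.

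The exposure definition is a second, smaller matter. A first-to-last span treats a pause as treatment, although the dates needed to remove it are collected.

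**Working it through.** The protocol states no figure to reproduce. Section 9.5 sets the 250 participants from prevalence and market conditions and gives no event rate.

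**Gaps.** Take 24 weeks of follow-up at the 10 mg once-daily dose named in 9.3.1, with an assumed 8-week pause.
- Span under 9.3.1: 24 × 7 = 168 days.
- Days treated: 168 − 8 × 7 = 112 days. The span overstates treated time by 168/112 = 1.5.
- Total dose net of the gap: 112 × 10 = 1120 mg. Divided by the span this gives 1120/168 = 6.7 mg/day, which is not a dose the participant took on any day.

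**Reverse causation.** Inputs from the protocol are 250 participants, 24 weeks (168 days), one dose level, and AEs counted to the end of the study. Everything else is assumed: AE risk 15% or 30% by week 24, 10% or 15% of participants stopping for unrelated reasons, and a varying share of AEs that stop the drug at onset. AE risk was unrelated to duration or dose. Model: logit P(AE) = a + b × (duration in days / 28), two-sided test at 5%, 1000 datasets per setting. The odds ratio (OR) is exp(b), per 4 weeks.

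| AEs that stop the drug | AE risk | Unrelated stops | Median OR per 4 weeks | Falsely inverse |
|---|---|---|---|---|
| 0% | 15% / 30% | 15% | 1.02 / 1.00 | 3% / 2% |
| 5% | 15% / 30% | 15% | 0.93 / 0.92 | 12% / 13% |
| 10% | 15% / 30% | 15% | 0.88 / 0.87 | 21% / 32% |
| 10% | 30% | 10% | 0.83 | 42% |
| 20% | 15% / 30% | 15% | 0.80 / 0.79 | 57% / 74% |
| 20% | 30% | 10% | 0.73 | 89% |

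With no AE-driven stops there is almost no bias, so the association comes from the stopping.

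**The three variables behave differently.**
- Without gaps, total dose is 10 mg × days, so it gives the same results as duration.
- With 10% AE-driven stops, 30% AE risk, 15% unrelated stops, and 28-day gaps in 30% of the other participants with an AE, the OR per 280 mg of total dose falls to 0.78 (71% falsely inverse). The duration OR stays at 0.87 (32%).
- A permanent stop leaves average daily dose at 10 mg. It varies only with interruptions or dose changes.

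**Dependence on AE recording.** If AEs were recorded only while on drug, the sign could reverse. At 30% AE risk and 15% unrelated stops, the OR is 1.43 / 1.18 / 1.05 / 0.90 for 0% / 5% / 10% / 20% AE-driven stops. Section 11.2 specifies collection to the end of the study, so the table is the relevant case.

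**A remedy that fails.** Cutting exposure at AE onset within the same logistic model shortens it for participants with an AE and for nobody else. With no AE stopping the drug and 10% unrelated stops, that model gives an OR of about 0.33 at 30% AE risk and 0.39 at 15%, falsely significant in 100% of datasets. Uncut duration at 30% risk gives 0.995 and 2.6%.

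**The case against.** The strongest objection is that no sentence puts duration or dose into the AE model. Section 9.7.2 leaves its continuous variables unnamed, and the only scope it states, for the tabulation, is demographics and baseline characteristics. Section 9.3.3 can be read as an inventory of collected items: it even lists a paediatric population although entry requires age 19 or over. Section 9.7 leaves full details to a statistical analysis plan that is not at hand. This stands to the extent that the bias is conditional. It does not remove the point, because the protocol itself classes these post-baseline variables as covariates, and 9.7.3 speaks of significant covariates, the term that heads 9.3.3. An analysis plan that follows the protocol inherits this.

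It is also fair that 9.7.2 reports incidence by participant. The first-to-last span is not the denominator of any stated outcome, total dose can be computed net of gaps from the dates collected, and the abstract calls all analyses exploratory. These points limit the consequence of the 9.3.1 definition and the weight of the regressions.

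A reader might infer that the plan will certainly produce a false inverse dose–AE result, or that all three variables are distorted alike. The documents do not support either. Use in the model is not stated, average daily dose is untouched by a permanent stop, and duration and total dose carry identical information only when there are no gaps.

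**Conclusion.** The point holds in conditional form. Section 9.3.1 counts interruptions as exposure, and 9.3.3 offers post-baseline duration and dose as covariates without keeping them out of the regressions in 9.7.2 and 9.7.3. If they are used there, AE-driven stopping can create a false inverse association of duration and total dose with AEs. With 5% of AEs stopping the drug the effect is modest. At 10% to 20% it is large enough to be reported as a finding in a fifth to nearly nine-tenths of datasets. These sizes rest on assumed AE risks and stopping rates, which the protocol does not give. The effective-rate regression is open to the same objection in principle, but no size was computed for it. The matter is worth correcting because the primary objective is safety and the data needed are already collected. The reported participant-level AE incidence is not affected.

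**What to change.** In 9.3.1, compute exposure as the sum of recorded intake periods, net of gaps, and report the first-to-last span separately.

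In 9.3.3, mark which items are baseline. In 9.7.2 and 9.7.3, restrict regression covariates to those, and report duration, total dose, average daily dose, follow-up duration and reasons for stopping descriptively only.

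If an exposure–AE relation is wanted, use a time-to-event model with time-varying exposure. Do not use a logistic model with exposure cut at AE onset.

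The cost is wording and programming on data already collected. A few odds ratios are dropped, and reported exposure becomes slightly shorter.

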9.4 DATA SOURCES

The source data will be captured from the medical records of the patients who have consented to data release. Details on how to capture the data are described in section 9.10.2.

9.5 STUDY SIZE

The enrolment target is 250 participants for a total of 2 years, considering the prevalence and market conditions in Korea.

9.6 DATA MANAGEMENT

Participants' data will be gathered by electronic Case Report Form (eCRF). The data management procedures to ensure the quality of the data are described in detail in the data management plan (DMP). Data management and statistics will be outsourced to a qualified CRO. DMP will be developed following BI and/or CRO relevant SOPs.

9.7 DATA ANALYSIS

The statistical analysis plan for the study is summarized below. Full details of the statistical analysis will be documented in the Statistical Analysis Plan (SAP), which will be finalized before the end of data collection.

ONIS New Data Collection Protocol

Page 21 of 54

Study number: 1245-0323 Document number: c42645766-03

Proprietary confidential information © 2024 Boehringer Ingelheim International GmbH or one or more of its affiliated companies

9.7.1 Analysis sets

250 participants will be entered in this study, and each participant will be followed for baseline, short term (12 weeks) follow-up, and long term (24 weeks) follow-up. The safety analysis will comprise all participants who took JARDIANCE® with at least one time of safety follow-up.

9.7.1.1 Number of participants who entered the study

This number means the actual number of participants as specified in the contract concluded with the investigator prior to initiation of the study.

9.7.1.2 Number of participants of CRF collection

This number means the number of participants who signed the data release consent form to participate in the study, with a record of taking JARDIANCE® once at least.

9.7.1.3 Number of participants for safety assessment

These include those who signed the data release consent form to participate in this study, took JARDIANCE® once at least, and were followed up by the investigator once or more. Reflecting the MFDS guideline, the cases below shall be excluded from safety analysis (defined below) set in the following order:

- a. Participants who did not signed (signature missing), or participants who signed on the data release consent form of JARDIANCE® CKD PMS prior to the contract date
- b. Participants who took JARDIANCE® prior to the contract date
- c. Participants who took JARDIANCE prior to signing the data release consent form
- d. Participants who have not taken JARDIANCE®
- e. Follow-up failure: Participants whose safety information cannot be obtained due to lost-to-follow-up
- f. Participants who were prescribed Jardiance for indications outside the local label

9.7.1.4 Number of participants for efficacy assessment

These cases include those who signed the data release consent form to participate in this study, had at least one follow-up visit, took Jardiance*, and had at least some follow-up data for the efficacy.

Reflecting the MFDS guideline, the cases below shall be excluded from efficacy analysis (defined below) set in the following order:

a. Participants excluded from the safety analysis set listed in section 9.7.1.3.

ONIS New Data Collection Protocol

Page 22 of 54

Study number: 1245-0323 **Document number: c42645766-03**

Proprietary confidential information © 2024 Boehringer Ingelheim International GmbH or one or more of its affiliated companies

b. Participants with missing information of efficacy assessment listed in section 9.3.2.2.

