'Effective' and 'ineffective' will be reported using numbers of participants, percentages with 95% CIs.

Categorical variable will be reported using numbers of participants, numbers of participants assessed as 'effective', effective rates and 95% CIs. Efficacy will be analyzed by Pearson's chisquire test or Fisher's exact test to determine if there are statistically significant differences.

Continuous variable will be reported using numbers of participants. Odds ratio and 95% CIs by simple logistic regression will be summarized.

To estimate any factors that are thought to influence an effective rate, logistic regression analysis and/or poisson regression will be conducted, and for statistically significant covariates the meaning will be described.

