9.7.5 Handling of missing data

Maximum attempt will be made to ensure the completeness of data collection. All available data will be used in the data analysis. Missing or incomplete dates of AEs are imputed according to BI standard.

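### Exclusion b ties the single efficacy set to UACR change, so investigator ratings from participants with no computable UACR change drop out of the effective-rate analyses

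*Protocol*

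**What the plan says.** Section 9.7.1.4 of the protocol builds the efficacy set in two steps. Its inclusion sentence requires consent, treatment, a follow-up visit and some follow-up efficacy data. It then lists exclusions, said to reflect the MFDS guideline. Exclusion a carries over the safety-set exclusions, and exclusion b removes "Participants with missing information of efficacy assessment listed in section 9.3.2.2".

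Section 9.3.2.2 contains a single outcome: "Change in UACR from baseline after 12 weeks and/or 24 weeks of treatment".

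The investigator's rating is listed elsewhere, in section 9.3.2.3 on further outcomes: "Investigator's overall efficacy assessment after 12 weeks and/or 24 weeks" of treatment. On how it is made, the protocol says: "The overall efficacy assessment is performed at the investigator's discretion". Its categories refer to the patient's clinical condition, and none requires a UACR value.

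Section 9.7.3 states: "Efficacy analyses will be performed on the efficacy set". Under that heading it continues: "For investigator's overall efficacy assessment, the number and percentage of participants will be presented". It then classifies ratings as effective or ineffective, gives percentages with 95% confidence intervals, compares subgroups by chi-square or Fisher's exact test, and fits logistic and/or Poisson regressions for the effective rate. No other analysis set is named for these results.

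**The concern.** The set that serves the rating is defined by the availability of a different outcome. A rating made in full at week 12 or week 24 does not count if the participant has no baseline UACR, or no UACR at either follow-up.

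Such gaps are plausible. The study is non-interventional, its data come from medical records (9.4), no eligibility criterion requires a UACR value (9.2.2.2, 9.2.2.3), and sites are meant to balance general hospitals and clinics (9.2.1), where testing habits may differ.

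Two things are at stake. Usable ratings are discarded from every analysis of the effective rate. The reported rate also describes only participants with a UACR change, without saying so. If having a UACR change is related to the rating, the rate differs from that among all rated participants. The results go to the regulator, so this denominator should be chosen on purpose and be visible.

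**Working it through.** **Cross-references**

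1. 9.7.1.4, exclusion b, points to 9.3.2.2 and to no other section.
2. 9.3.2.2 holds UACR change only. Because either time point is enough, a participant is excluded only if no change can be computed: no baseline, or no follow-up value at both week 12 and week 24.
3. 9.3.2.3 holds the rating, which can be made without a UACR value.
4. 9.7.3 assigns efficacy analyses to the efficacy set and specifies the rating analyses with no exception.

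It follows that a rated participant with no computable UACR change is excluded from the rating analyses.

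**Size (illustration only)**

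The protocol has no figure to reproduce. The 250 in section 9.5 rests on prevalence and market conditions, and no expected effective rate or UACR missingness is given.

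Inputs:
- N = 250, the enrolment target (9.5), with all participants taken as rated. This is an upper limit.
- m, the share of rated participants with no UACR change: assumed 10–40%.
- p, the effective rate: assumed 70%.
- d, the difference in effective rate between participants with and without a UACR change: assumed 10–20 points, sign unknown.

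Formulas:
- Ratings lost = m × N; remaining n = (1 − m) × N.
- 95% half-width = 1.96 × √(p(1 − p)/n).
- Shift = rate in tested − rate in all rated = p_t − [(1 − m)p_t + m·p_u] = m × (p_t − p_u), so its size is m × d.

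With all 250 ratings the half-width is 1.96 × √(0.21/250) = 5.68 points.

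| m | Ratings lost | n | Half-width at 70% (points) | Increase (points) | Shift for d = 10 to 20 (points, either sign) |
|---|---|---|---|---|---|
| 10% | 25 | 225 | 5.99 | 0.31 | 1 to 2 |
| 20% | 50 | 200 | 6.35 | 0.67 | 2 to 4 |
| 30% | 75 | 175 | 6.79 | 1.11 | 3 to 6 |
| 40% | 100 | 150 | 7.33 | 1.65 | 4 to 8 |

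The loss of precision is small across the range. The possible shift is larger, but it needs both a sizeable m and a real difference between the two groups.

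**The case against.** **The loss may be small.** UACR is scheduled at all three visits without the availability flag given to other laboratory tests (9.2.5). Baseline may come from up to 6 months earlier, no window limit is stated for follow-up values, and one follow-up value suffices. This stands: m could be below the illustrated range.

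**The rated number will be below 250.** Safety-set exclusions and loss to follow-up act first, and unassessable ratings are classed as neither effective nor ineffective. This also stands, so the counts above are upper limits for each m.

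**The rule may reflect the MFDS guideline.** The guideline is not reproduced, so this cannot be excluded. But nothing in the protocol says that the rating must depend on UACR.

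**A common set has a use.** It lets UACR change and rating be read on the same participants. That is a legitimate preference, but the protocol does not give it as the reason, and it can be met by a supplementary table.

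**Full detail is deferred to the SAP.** That is so for much else, but the protocol fixes this exclusion itself.

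A reader might also infer that the protocol flatly contradicts itself, because the inclusion sentence is broader than exclusion b and because section 9.7.5 says "All available data will be used in the data analysis". That goes too far. Exclusions normally narrow an inclusion sentence, and the safety set is built the same way. The line in 9.7.5 concerns missing data; if it overrode set definitions, it would conflict with every exclusion. The broader inclusion sentence suggests at most that exclusion b was drafted more narrowly than intended.

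**Conclusion.** The point holds as a flaw in a stated rule. Followed literally, exclusion b removes valid investigator ratings from participants with no computable UACR change, for a reason unrelated to the rating.

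The size is unknown. With 250 rated and 10–40% lacking a UACR change, 25–100 ratings are lost, the half-width at a 70% rate goes from 5.7 to 6.0–7.3 points, and the effective rate could move by 1–8 points if the groups differ by 10–20 points. The missingness, the rate and the difference are all assumptions.

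A reader might infer that the effective rate will be overstated. The protocol does not support a direction: nothing in it says that untested participants are rated worse, and the shift could be zero or negative.

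The consequence is limited. The rating is a further outcome in a study whose analyses are all exploratory. The primary safety results are untouched, and the UACR results do not change, because participants without a UACR change could not contribute to them.

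**What to change.** Reword exclusion b in 9.7.1.4 so that it removes participants missing the outcome being analysed. Then:

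- UACR change and albuminuria category use safety-set participants with a baseline and at least one follow-up UACR.
- The investigator's overall assessment uses all safety-set participants with a recorded assessment, whether or not UACR was measured.
- Efficacy tables show both Ns.

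This takes one sentence in the protocol, carried into the SAP, and no new data. The downside is two denominators in the efficacy tables. Before adopting it, the sponsor should confirm that the wording fits the MFDS guideline cited in 9.7.1.4.
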